Appendix 4 Management of atezolizumab-specific adverse events

Note: This appendix is a redacted version of the detailed guidance for the management of immune-related AEs, located in the atezolizumab IB (Edition 17), which should be consulted for further guidance.

Pulmonary events including pneumonitis	
Event	Management
Grade 1	Continue atezolizumab and monitor closely.
Grade 2	
 Withhold atezolizumab for up to 12 weeks after event onset. Refer patient to pulmonary and infectious disease specialists and consider bronchoscopy or bronchoscopic alveolar lavage. Initiate treatment with corticosteroids equivalent to 1-2 mg/kg/day oral prednisone. If event resolves to Grade 1 or better, resume atezolizumab. If event does not resolve to Grade 1, permanently discontinue atezolizumab and contact Medical Monitor. For recurrent events, treat as a Grade 3 or 4 event.
Grade 3 or 4	
 Permanently discontinue atezolizumab and contact Medical Monitor. Bronchoscopy or bronchoscopic alveolar lavage is recommended. Initiate treatment with corticosteroids equivalent to 1-2 mg/kg/day oral prednisone, and consider adding an immunosuppressive agent if event does not improve within 48 hours after initiating corticosteroids. If event resolves to Grade 1 or better, taper corticosteroids over ≥ 1 month.

Hepatic events	
Event	Management
Grade 1	Continue atezolizumab and monitor liver function tests (LFTs) until values resolve to normal or to baseline values.
Grade 2	
All events:
 
 Monitor LFTs more frequently until return to baseline values. 
Events with a duration of > 5 days
 
 Withhold atezolizumab for up to 12 weeks after event onset. Initiate treatment with corticosteroids equivalent to 1-2 mg/kg/day oral prednisone. If event resolves to Grade 1 or better, resume atezolizumab. If event does not resolve to Grade 1, permanently discontinue atezolizumab and contact Medical Monitor.

Hepatic events	
Event	Management
Grade 3 or 4	
 • Permanently discontinue atezolizumab and contact Medical Monitor. • Consider patient referral to GI specialist for evaluation and liver biopsy to establish etiology of hepatic injury. • Initiate treatment with corticosteroids equivalent to 1-2 mg/kg/day oral prednisone, and consider adding an immunosuppressive agent if event does not improve within 48 hours after initiating corticosteroids. • If event resolves to Grade 1 or better, taper corticosteroids over ≥ 1 month.

Gastrointestinal events (diarrhea or colitis)	
Event	Management
Grade 1	
 • Continue atezolizumab and monitor closely. • Initiate symptomatic treatment. • Endoscopy is recommended if symptoms persist for > 7 days.
Grade 2	
 • Withhold atezolizumab for up to 12 weeks after event onset. • Initiate symptomatic treatment. • Patient referral to GI specialist is recommended. • For recurrent events or events that persist > 5 days, initiate treatment with corticosteroids equivalent to 1-2 mg/kg/day oral prednisone. • If event resolves to Grade 1 or better, resume atezolizumab. • If event does not resolve to Grade 1, permanently discontinue atezolizumab and contact Medical Monitor.
Grade 3	
 • Withhold atezolizumab for up to 12 weeks after event onset. • Refer patient to GI specialist for evaluation and confirmatory biopsy. • Initiate treatment with corticosteroids equivalent to 1-2 mg/kg/day IV methylprednisolone and convert to 1-2 mg/kg/day oral prednisone or equivalent upon improvement. • If event resolves to Grade 1 or better, resume atezolizumab. • If event does not resolve to Grade 1, permanently discontinue atezolizumab and contact Medical Monitor.
Grade 4	
 • Permanently discontinue atezolizumab and contact Medical Monitor. • Consider patient referral to GI specialist for evaluation and confirmatory biopsy. • Initiate treatment with corticosteroids equivalent to 1-2 mg/kg/day oral prednisone, and consider adding an immunosuppressive agent if event does not improve within 48 hours after initiating corticosteroids. • If event resolves to Grade 1 or better, taper corticosteroids over ≥ 1 month.

Endocrine Events	
Event	Management
Asymptomatic hypothyroidism	
 Continue atezolizumab. Initiate treatment with thyroid replacement hormone, monitor TSH weekly.
Symptomatic hypothyroidism	
 Withhold atezolizumab. Initiate treatment with thyroid replacement hormone, monitor TSH weekly. Consider patient referral to endocrinologist. Resume atezolizumab when symptoms are controlled and thyroid function is improving.
Asymptomatic hyperthyroidism	
TSH \geq 0.1 mU/L and $<$ 0.5 mU/L:
 
 Continue atezolizumab, and monitor TSH every 4 weeks. 
TSH $<$ 0.1 mU/L:
 
 Follow guidelines for symptomatic hyperthyroidism.
Symptomatic hyperthyroidism	
 Withhold atezolizumab. Initiate treatment with anti-thyroid drug such as methimazole or carbimazole as needed. Consider patient referral to endocrinologist. Resume atezolizumab when symptoms are controlled and thyroid function is improving. Permanently discontinue atezolizumab and contact Medical Monitor for life-threatening immune-mediated hyperthyroidism.
Symptomatic adrenal insufficiency, Grades 2-4	
 Withhold atezolizumab for up to 12 weeks after event onset. Refer patient to endocrinologist. Perform appropriate imaging. Initiate treatment with corticosteroids equivalent to 1-2 mg/kg/day IV methylprednisolone and convert to 1-2 mg/kg/day oral prednisone or equivalent upon improvement. If event resolves to Grade 1 or better and patient is stable on replacement therapy, resume atezolizumab. If event does not resolve to Grade 1 or better or patient is not stable on replacement therapy while withholding atezolizumab, permanently discontinue atezolizumab and contact Medical Monitor.
Hyperglycemia, Grade 1 or 2	
 Continue atezolizumab and monitor for glucose control. Investigate for diabetes. If patient has Type 1 diabetes, treat as a Grade 3 event. If patient does not have Type 1 diabetes, treat as per institutional guidelines.
Hyperglycemia, Grade 3 or 4	
 Withhold atezolizumab and monitor for glucose control. Initiate treatment with insulin. Resume atezolizumab when symptoms resolve and glucose levels are stable.
Hypophysitis (pan-	
 Withhold atezolizumab for up to 12 weeks after event onset.

Endocrine Events	
Event	Management
hypopituitarism), Grade 2 or 3	
 • Refer patient to endocrinologist. • Perform brain MRI (pituitary protocol). • Initiate treatment with corticosteroids equivalent to 1-2 mg/kg/day IV methylprednisolone and convert to 1-2 mg/kg/day oral prednisone or equivalent upon improvement. • Initiate hormone replacement if clinically indicated. • If event resolves to Grade 1 or better, resume atezolizumab. • If event does not resolve to Grade 1 or better while withholding atezolizumab, permanently discontinue atezolizumab and contact Medical Monitor. • For recurrent hypophysitis, treat as a Grade 4 event.
Hypophysitis (pan- hypopituitarism), Grade 4	
 • Permanently discontinue atezolizumab and contact Medical Monitor. • Refer patient to endocrinologist. • Perform brain MRI (pituitary protocol). • Initiate treatment with corticosteroids equivalent to 1-2 mg/kg/day IV methylprednisolone and convert to 1-2 mg/kg/day oral prednisone or equivalent upon improvement. • Initiate hormone replacement if clinically indicated.

Ocular Events	
Event	Management
Grade 1	
 • Continue atezolizumab. • Patient referral to ophthalmologist is strongly recommended. • Initiate treatment with topical corticosteroid eye drops and topical immunosuppressive therapy. • If symptoms persist, treat as a Grade 2 event.
Grade 2	
 • Withhold atezolizumab for up to 12 weeks after event onset. • Patient referral to ophthalmologist is strongly recommended. • Initiate treatment with topical corticosteroid eye drops and topical immunosuppressive therapy. • If event resolves to Grade 1 or better, resume atezolizumab. • If event does not resolve to Grade 1, permanently discontinue atezolizumab and contact Medical Monitor.
Grade 3 or 4	
 • Permanently discontinue atezolizumab and contact Medical Monitor. • Refer patient to ophthalmologist. • Initiate treatment with corticosteroids equivalent to 1-2 mg/kg/day oral prednisone. • If event resolves to Grade 1 or better, taper corticosteroids over ≥ 1 month.

Ocular Events	
Event	Management
Immune-mediated myocarditis	
Event	Management
Grade 2	
 • Withhold atezolizumab for up to 12 weeks after event onset and contact Medical Monitor. • Refer patient to cardiologist, initiate treatment as per institutional guidelines and consider antiarrhythmic drugs, temporary pacemaker, ECMO, or VAD as appropriate. • Consider treatment with corticosteroids equivalent to 1-2 mg/kg/day IV methylprednisolone and convert to 1-2 mg/kg/day oral prednisone or equivalent upon improvement. • If event resolves to Grade 1 or better, resume atezolizumab. • If event does not resolve to Grade 1 or better while withholding atezolizumab, permanently discontinue atezolizumab and contact Medical Monitor.
Grade 3 or 4	
 • Permanently discontinue atezolizumab and contact Medical Monitor. • Refer patient to cardiologist, initiate treatment as per institutional guidelines and consider antiarrhythmic drugs, temporary pacemaker, ECMO, or VAD as appropriate. • Consider treatment with corticosteroids equivalent to 1-2 mg/kg/day IV methylprednisolone and convert to 1-2 mg/kg/day oral prednisone or equivalent upon improvement. • If event does not improve within 48 hours after initiating corticosteroids, consider adding an immunosuppressive agent. • If event resolves to Grade 1 or better, taper corticosteroids over ≥ 1 month.

Infusion-related reactions (IRR) and cytokine-release syndrome (CRS)	
Event	Management
Grade 1 (fever with or without constitutional symptoms)	
 • Immediately interrupt infusion. • Upon symptom resolution, wait for 30 minutes and then restart infusion at half the rate being given at the time of event onset. • If the infusion is tolerated at the reduced rate for 30 minutes, the infusion rate may be increased to the original rate. • If symptoms recur, discontinue infusion of this dose. • Administer symptomatic treatment, including maintenance of IV fluids for hydration. • In case of rapid decline or prolonged CRS (> 2 days) or in patients with significant symptoms and/or comorbidities, consider managing as per Grade 2. • For subsequent infusions, consider administration of oral premedication with antihistamines, anti-pyretics, and/or analgesics, and monitor closely for IRRs and/or CRS.

Infusion-related reactions (IRR) and cytokine-release syndrome (CRS)	
Event	Management

Grade 2 (fever with hypotension not requiring vasopressors and/or hypoxia requiring low-flow oxygen by nasal cannula or blow-by)
	
 • Immediately interrupt infusion. • Upon symptom resolution, wait for 30 minutes and then restart infusion at half the rate being given at the time of event onset. • If the infusion is tolerated at the reduced rate for 30 minutes, the infusion rate may be increased to the original rate. • If symptoms recur, discontinue infusion of this dose. • Administer symptomatic treatment, including maintenance of IV fluids for hydration. • In case of rapid decline or prolonged CRS (> 2 days) or in patients with significant symptoms and/or comorbidities, consider managing as per Grade 2. • For subsequent infusions, consider administration of oral premedication with antihistamines, anti-pyretics, and/or analgesics, and monitor closely for IRRs and/or CRS.

Grade 3 (fever with hypotension requiring a vasopressor [with or without vasopressin] and/or hypoxia requiring high-flow oxygen by nasal cannula, face mask, non-rebreather mask, or venture mask)
	
 • Permanently discontinue atezolizumab and contact Medical Monitor. • Administer symptomatic treatment. For hypotension, administer IV fluid bolus and vasopressor as needed. • Monitor cardiopulmonary and other organ function closely; monitoring in the ICU is recommended. Administer IV fluids as clinically indicated, and manage constitutional symptoms and organ toxicities as per institutional practice. • Rule out other inflammatory conditions that can mimic CRS (e.g., sepsis). If no improvement within 24 hours, initiate workup and assess for signs and symptoms of HLH or MAS. • Administer IV corticosteroids (e.g., methylprednisolone 2 mg/kg/day or dexamethasone 10 mg every 6 hours). Consider anti-cytokine therapy. • Hospitalize patient until complete resolution of symptoms. If no improvement within 24 hours, manage as per Grade 4, that is, admit patient to ICU and initiate hemodynamic monitoring, mechanical ventilation, and/or IV fluids and vasopressors as needed; for patients who are refractory to anti-cytokine therapy, experimental treatments may be considered at the discretion of the investigator and in consultation with the Medical Monitor.

Grade 4 (fever with hypotension requiring multiple vasopressors [excluding Vasopressin] and/or hypoxia requiring oxygen by positive pressure [e.g., CPAP, BiPAP, intubation and mechanical ventilation])
	
 • Permanently discontinue atezolizumab and contact Medical Monitor. • Administer symptomatic treatment. • Admit patient to ICU and initiate hemodynamic monitoring, mechanical ventilation, and/or IV fluids and vasopressors as needed. Monitor other organ function closely. Manage constitutional symptoms and organ toxicities as per institutional practice. • Rule out other inflammatory conditions that can mimic CRS (e.g., sepsis). If no improvement within 24 hours, initiate workup and assess for signs and symptoms of HLH or MAS. • Administer IV corticosteroids (e.g., methylprednisolone 2 mg/kg/day or dexamethasone 10 mg every 6 hours).

Infusion-related reactions (IRR) and cytokine-release syndrome (CRS)	
Event	Management
	
 Consider anti-cytokine therapy. For patients who are refractory to anti-cytokine therapy, experimental treatments may be considered at the discretion of the investigator and in consultation with the Medical Monitor. Hospitalize patient until complete resolution of symptoms.

Pancreatic events including pancreatitis	
Event	Management
Amylase and/or lipase elevation, Grade 2	
Amylase and/or lipase > 1.5-2.0 × ULN:
 
 Continue atezolizumab and monitor amylase / lipase weekly. For prolonged elevation (e.g., > 3 weeks), consider treatment with corticosteroids equivalent to 10 mg/day oral prednisone. 
Asymptomatic with amylase and/or lipase > 2.0-5.0 × ULN:
 
 Treat as Grade 3.
Amylase and/or lipase elevation, Grade 3 or 4	
 Withhold atezolizumab for up to 12 weeks after event onset, and monitor amylase and lipase every other day. Refer patient to GI specialist. If no improvement, consider treatment with corticosteroids equivalent to 1-2 mg/kg/day oral prednisone. If event resolves to Grade 1 or better, resume atezolizumab. If event does not resolve to Grade 1, permanently discontinue atezolizumab and contact Medical Monitor. For recurrent events, permanently discontinue atezolizumab and contact Medical Monitor.
Immune-mediated pancreatitis, Grade 2 or 3	
 Withhold atezolizumab for up to 12 weeks after event onset. Refer patient to GI specialist. Initiate treatment with corticosteroids equivalent to 1-2 mg/kg/day IV methylprednisolone and convert to 1-2 mg/kg/day oral prednisone or equivalent upon improvement. If event resolves to Grade 1 or better, resume atezolizumab. If event does not resolve to Grade 1, permanently discontinue atezolizumab and contact Medical Monitor. For recurrent events, permanently discontinue atezolizumab and contact Medical Monitor.
Immune-mediated pancreatitis, Grade 4	
 Permanently discontinue atezolizumab and contact Medical Monitor. Refer patient to GI specialist. Initiate treatment with corticosteroids equivalent to 1-2 mg/kg/day IV methylprednisolone and convert to 1-2 mg/kg/day oral prednisone or equivalent upon improvement.

Pancreatic events including pancreatitis	
Event	Management
	
 • If event does not improve within 48 hours after initiating corticosteroids, consider adding an immunosuppressive agent. • If event resolves to Grade 1 or better, taper corticosteroids over ≥ 1 month.

Dermatologic events	
Event	Management
Grade 1	
 • Continue atezolizumab. • Consider treatment with topical corticosteroids and/or other symptomatic therapy (e.g., antihistamines).
Grade 2	
 • Continue atezolizumab. • Consider patient referral to dermatologist. • Initiate treatment with topical corticosteroids. • Consider treatment with higher-potency topical corticosteroids if event does not improve.
Grade 3	
 • Withhold atezolizumab for up to 12 weeks after event onset. • Refer patient to dermatologist. • Initiate treatment with corticosteroids equivalent to 10 mg/day oral prednisone, increasing dose to 1-2 mg/kg/day if event does not improve within 48-72 hours. • If event resolves to Grade 1 or better, resume atezolizumab. • If event does not resolve to Grade 1 or better while withholding atezolizumab, permanently discontinue atezolizumab and contact Medical Monitor.
Grade 4	Permanently discontinue atezolizumab and contact Medical Monitor.

Neurologic Disorders	
Event	Management
Immune-mediated neuropathy, Grade 1	
 • Continue atezolizumab. • Investigate etiology.
Immune-mediated neuropathy, Grade 2	
 • Withhold atezolizumab for up to 12 weeks after event onset. • Investigate etiology. • Initiate treatment as per institutional guidelines. • If event resolves to Grade 1 or better, resume atezolizumab. • If event does not resolve to Grade 1, permanently discontinue atezolizumab and contact Medical Monitor.
Immune-mediated	
 • Permanently discontinue atezolizumab and contact Medical Monitor.

Neurologic Disorders	
Event	Management
neuropathy, Grade 3 or 4	
 Initiate treatment as per institutional guidelines.
Myasthenia gravis and Guillain-Barré syndrome (any grade)	
 Permanently discontinue atezolizumab and contact Medical Monitor. Refer patient to neurologist. Initiate treatment as per institutional guidelines. Consider initiation of corticosteroids equivalent to 1-2 mg/kg/day oral or IV prednisone.

Immune-mediated meningoencephalitis	
Event	Management
All grades	
 Permanently discontinue atezolizumab and contact Medical Monitor. Refer patient to neurologist. Initiate treatment with corticosteroids equivalent to 1-2 mg/kg/day IV methylprednisolone and convert to 1-2 mg/kg/day oral prednisone or equivalent upon improvement. If event does not improve within 48 hours after initiating corticosteroids, consider adding an immunosuppressive agent. If event resolves to Grade 1 or better, taper corticosteroids over \geq 1 month.

Renal Events	
Event	Management
Grade 1	
 Continue atezolizumab. Monitor kidney function closely, including creatinine, until values resolve to within normal limits or to baseline values.
Grade 2	
 Withhold atezolizumab for up to 12 weeks after event onset. Refer patient to renal specialist. Initiate treatment with corticosteroids equivalent to 1-2 mg/kg/day oral prednisone. If event resolves to Grade 1 or better, resume atezolizumab. If event does not resolve to Grade 1 or better while withholding atezolizumab, permanently discontinue atezolizumab and contact Medical Monitor.

Renal Events	
Event	Management
Grade 3 or 4	
 • Permanently discontinue atezolizumab and contact Medical Monitor. • Refer patient to renal specialist and consider renal biopsy. • Initiate treatment with corticosteroids equivalent to 1-2 mg/kg/day oral prednisone. • If event does not improve within 48 hours after initiating corticosteroids, consider adding an immunosuppressive agent. • If event resolves to Grade 1 or better, taper corticosteroids over \geq 1 month.

Immune-Mediated Myositis	
Event	Management
Grade 1	
 • Continue atezolizumab. • Refer patient to rheumatologist or neurologist. • Initiate treatment as per institutional guidelines.
Grade 2	
 • Withhold atezolizumab for up to 12 weeks after event onset, and contact Medical Monitor. • Refer patient to rheumatologist or neurologist. • Initiate treatment as per institutional guidelines. • Consider treatment with corticosteroids equivalent to 1-2 mg/kg/day IV methylprednisolone and convert to 1-2 mg/kg/day oral prednisone or equivalent upon improvement. • If corticosteroids are initiated and event does not improve within 48 hours after initiating corticosteroids, consider adding an immunosuppressive agent. • If event resolves to Grade 1 or better, resume atezolizumab. • If event does not resolve to Grade 1 or better while withholding atezolizumab, permanently discontinue atezolizumab and contact Medical Monitor.
Grade 3	
 • Withhold atezolizumab for up to 12 weeks after event onset, and contact Medical Monitor. • Refer patient to rheumatologist or neurologist. • Initiate treatment as per institutional guidelines. • Respiratory support may be required in more severe cases. • Initiate treatment with corticosteroids equivalent to 1-2 mg/kg/day IV methylprednisolone, or higher-dose bolus if patient is severely compromised (e.g., cardiac or respiratory symptoms, dysphagia, or weakness that severely limits mobility); convert to 1-2 mg/kg/day oral prednisone or equivalent upon improvement. • If event does not improve within 48 hours after initiating corticosteroids, consider adding an immunosuppressive agent. • If event resolves to Grade 1 or better, resume atezolizumab.

Immune-Mediated Myositis	
Event	Management
	
 • If event does not resolve to Grade 1 or better while withholding atezolizumab, permanently discontinue atezolizumab and contact Medical Monitor. • For recurrent events, treat as Grade 4 event. Permanently discontinue atezolizumab and contact Medical Monitor.
Grade 4	
 • Permanently discontinue atezolizumab and contact Medical Monitor. • Refer patient to rheumatologist or neurologist. • Initiate treatment as per institutional guidelines. • Respiratory support may be required in more severe cases. • Initiate treatment with corticosteroids equivalent to 1-2 mg/kg/day IV methylprednisolone, or higher-dose bolus if patient is severely compromised (e.g., cardiac or respiratory symptoms, dysphagia, or weakness that severely limits mobility); convert to 1-2 mg/kg/day oral prednisone or equivalent upon improvement. • If event does not improve within 48 hours after initiating corticosteroids, consider adding an immunosuppressive agent. • If event resolves to Grade 1 or better, taper corticosteroids over ≥ 1 month.

Suspected hemophagocytic lymphohistiocytosis (HLH) or macrophage activation syndrome (MAS)	
Event	Management
Suspected HLH or MAS	
 • Permanently discontinue atezolizumab and contact Medical Monitor. • Consider patient referral to hematologist. • Initiate supportive care, including intensive care monitoring if indicated per institutional guidelines. • Consider initiation of IV corticosteroids, an immunosuppressive agent, and/or anti-cytokine therapy. • If event does not respond to treatment within 24 hours, contact Medical Monitor and initiate treatment as appropriate according to published guidelines (La Rosée 2015; Schram 2015; La Rosée 2019). • If event resolves to Grade 1 or better, taper corticosteroids over ≥ 1 month.

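### Appendix 4: the escalation line for grade 2 infusion reaction/CRS points back to grade 2, so a declining patient short of the grade 3 definition has no written step up

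*Protocol*

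**What the plan says.** The IRR/CRS table in Protocol Appendix 4 has one row per grade. Grade 1 is fever with or without constitutional symptoms. Grade 2 adds hypotension that does not need vasopressors, hypoxia managed with low-flow oxygen, or both. Grade 3 begins at "fever with hypotension requiring a vasopressor" or at a need for high-flow oxygen.

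The grade 1 and grade 2 rows each contain a line that opens "In case of rapid decline or prolonged CRS (> 2 days" and ends by directing that "patients with significant symptoms and/or comorbidities, consider managing as per Grade 2". The grade 3 row has its own escalation line: "If no improvement within 24 hours, manage as per Grade 4".

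Sections 4.5.1 and 6.1.2.6 of the Protocol send sites to Appendix 4 for atezolizumab toxicity and add no IRR/CRS rule of their own. The note at the head of the appendix describes it as a redacted version of guidance in the atezolizumab IB (Edition 17), "which should be consulted for further guidance".

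**The concern.** An escalation line is useful only if it leads to a different set of actions. In the grade 1 row the reference to grade 2 is a step up in name. In the grade 2 row the same reference is circular.

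The line is meant for patients who look worse than their formal grade: those declining quickly, those whose CRS has lasted more than two days, and those with significant symptoms or comorbidities. At grade 2 these patients are already hypotensive or hypoxic. The actions they might need early appear in this table only from grade 3: permanent discontinuation of atezolizumab, contact with the Medical Monitor, IV corticosteroids, consideration of anti-cytokine therapy, recommended ICU monitoring and hospitalization. As printed, nothing in the grade 2 row prompts a site to consider them before the grade 3 definition is met.

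**Working it through.** The plan states no figure on this point, so the check compares text.

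**Step 1. Compare the two rows.** The grade 1 and grade 2 rows have seven bullets each, in the same order:

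1. interrupt the infusion
2. restart at half rate once symptoms resolve
3. return to full rate if tolerated
4. stop this dose if symptoms recur
5. treat symptoms and maintain fluids
6. the escalation line
7. consider premedication next time

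The wording is identical in 7 of 7. The grade 1 step up to grade 2 therefore also changes nothing in practice.

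**Step 2. List every redirect to a named grade in Appendix 4.**

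| Event | From | To |
|---|---|---|
| Pulmonary ("For recurrent events, treat as a Grade 3 or 4 event") | 2 | 3 or 4 |
| Hyperglycemia | 1 or 2 | 3 |
| Hypophysitis | 2 or 3 | 4 |
| Ocular ("If symptoms persist, treat as a Grade 2 event") | 1 | 2 |
| IRR/CRS | 1 | 2 |
| **IRR/CRS** | **2** | **2** |
| IRR/CRS | 3 | 4 |
| Amylase/lipase ("Treat as Grade 3") | 2 | 3 |
| Myositis | 3 | 4 |

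There are nine redirects. Eight go to a higher grade and one goes to its own grade.

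**Step 3. Look for a route elsewhere.** Section 4.5.1 refers to Appendix 4. Section 6.1.2.6 allows temporary or permanent discontinuation for the toxicities in the appendix but sets no grade 2 to grade 3 step. Section 1.4.3.2 refers in general terms to current checkpoint-inhibitor guidelines. None of these supplies the missing step.

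**Step 4. Bound the gap.** A patient who meets the vasopressor or high-flow oxygen criterion moves to the grade 3 row by definition. The uncovered patient meets a trigger in the escalation line but not that criterion.

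**Step 5. Exposure.** Substudy 3 plans 36 evaluable patients and Cohort 4b plans 50, so 36 + 50 = 86 if both complete Stage 2, plus any crossover patients from Cohort 4a. If both stop at Stage 1, the total is 18 + 16 = 34. The documents give no grade 2 IRR/CRS rate. For illustration only, assume 1% to 5% per patient:

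| Patients | Expected number (1% to 5%) | Chance of at least one: 1 − (1 − rate)^n |
|---|---|---|
| 86 | 0.9 to 4.3 | 58% to 99% |
| 34 | 0.3 to 1.7 | 29% to 83% |

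These figures count any grade 2 event managed under the row. The share of such patients who would decline without meeting grade 3 is unknown, and the conclusion does not rest on the assumed rates.

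**The case against.** The strongest reply has five parts.

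- **The duplication could come from reading the PDF.** The two rows fall on either side of a repeated table header. This is unlikely, because the grade 2 row carries its own distinct definition. A look at the printed page would settle it.
- **Other provisions narrow the gap.** Section 6.1.2.6 permits discontinuation without limiting it to grade 3. Section 7.2.6 requires 24-hour reporting of immune-related events from grade 2, which would bring early sponsor contact if CRS is classed as immune-related. Section 6.4.2 allows systemic corticosteroids for immune-related events while atezolizumab is withheld. Appendix 4 has a separate row for suspected HLH or MAS. Section 7.4.1 leaves each patient's safety with the Investigator. These points stand as mitigation. None corrects the printed line or tells a site that it is wrong.
- **The row does not tell sites to re-infuse a declining patient.** This is right: restart is conditional on symptoms resolving, and recurrence stops that dose. The defect is a missing prompt to escalate, not an instruction to continue.
- **The eight upward redirects have mixed triggers.** Some concern recurrence, a diagnosis or a laboratory threshold, and only three concern worsening or failure to improve. That weakens the pattern as evidence for the intended wording. It does not make a self-referring line meaningful.
- **Grade 3 as the intended target is an inference.** The IB is not available here. This is also right, and it is why the correction should be confirmed against the IB.

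**Conclusion.** The concern holds. The grade 2 IRR/CRS escalation line is circular as written, and the appendix contains no step from grade 2 to grade 3 management before the grade 3 definition is met. This is a drafting error in an operative safety instruction and should be fixed.

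Its reach is limited to atezolizumab-treated patients with grade 2 IRR/CRS who are deteriorating, prolonged or symptomatic but still short of grade 3. The number of such patients cannot be estimated from the documents. The affected line is advisory, and clinicians keep their judgment.

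Only the self-referring line is shown to be wrong from the text. The other six repeated bullets may or may not be intended. That the line should name grade 3 rests on the step-up in the neighbouring rows. There is no consequence for sample size, error rates or the DLT analysis.

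**What to change.** In the grade 2 IRR/CRS row of Appendix 4, change the grade named in the escalation line from 2 to 3, and confirm that wording against the atezolizumab IB (Edition 17). Check the row's other six bullets against the same source and correct only those that were carried over from grade 1 in error. Notify sites of the corrected row.

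The cost is one line in one table row, a short check against the IB and a site notification. Design and analysis are unchanged.
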